2 STUDY SUMMARY

2.1 Protocol Summary Table

Protocol Title & Number	Exploratory trial to improve postextubation management for patients at risk for extubation failure IRB# 1332767
Study Short Title	GMC – [name] – Postextubation Management Pilot
Research Method	Prospective Interventional
Therapeutic Area	Pulmonary/Critical Care
Department	Intensive Care Unit, Critical Care Unit, 4 East
Study Description	This is an exploratory study designed to gather baseline information to determine the effectiveness of a standardized postextubation management protocol in a subset of patients at risk for reintubation.
Primary Endpoints	
• Proportion of patients that require reintubation within 72 hours• Association between reintubation rates and patient demographics or characteristics
Secondary Endpoints	
• Length of stay (ICU and total)• Ventilator time• In-hospital mortality• In-hospital adverse event rate• 30-day readmission rate
Prospective Cohort Study Population ^a	This study will include up to 40 mechanically ventilated, adult patients considered at-risk for re-intubation. See Section 6.3 . for detailed inclusion criteria.
Intervention(s)	
• Early NIV via BiPAP• High Flow Nasal Cannula breaks from NIV• Wean after 24 hours
Duration	Intervention Duration – Approximately 24 hours Study Duration – 3 months Participant Duration- total hospital stay, estimated at 14.1 ± 16.9 days (American Association for the Surgery of Trauma, 2011).

^a Data for this study will be compared to a historical control cohort, comprising mechanically ventilated, high-risk patients who underwent standard of care postextubation management.

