4 SPECIFIC AIMS

The purpose of this study is to establish baseline data regarding the institutional reintubation rate in a specific, high-risk patient population of interest and to determine the preliminary effectiveness of a standardized intermittent NIV/HFNC protocol in patients considered high risk for reintubation. This is a prospective, non-randomized exploratory trial with the following specific aim(s):

Aim 1. Compare reintubation rates (within 72 hours) between patients that undergo a standardized, intermittent NIV/HFNC protocol and a historical control cohort.

Aim 2. Determine whether reintubation rates differ as a function of age, gender, co-morbidity, reason for intubation, service line/operative status, or modified RSBI.

Secondary aims include calculating length of stay (ICU and total hospital), total ventilator time, in-hospital mortality rate, adverse event rates, and 30-day readmission rate. The overall demographics of the interventional group will also be compared to the historical control cohort.

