7.1 Statistical Analysis Plan

In general, categorical variables will be summarized with counts and percentages; and continuous variables will be summarized with means, standard deviations, medians and ranges. The two groups will be compared on categorical variables using chi-square tests, or Fisher's exact tests if the data in the contingency table have cells with expected frequency of $n < 5$. The two groups will be compared on the continuous variables using a t-test if the variable is approximately normally distributed or using a Wilcoxon rank sum test if the variable is markedly non-normally distributed. These general statistical methods will be used to compare groups on all the demographics and baseline characteristics, for the intention to treat (ITT) and per protocol (PP) populations.

Results will be considered statistically significant if the p-value is less than or equal to 0.05. SAS V9.3 or higher will be used for all summary statistics and statistical analyses.

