7.1.1 Primary Statistical Analysis Methods

Because this is a non-randomized study, it is assumed that there will be some differences between groups on the demographics and/or baseline characteristics. Therefore logistic regression modeling

techniques will be used for the primary statistical analyses. This will allow for comparison of the groups on reintubation rate while adjusting out baseline differences.

The primary analysis is comparison of the groups on reintubation rates within 72 hours on the ITT population. Potential differences between groups on demographic and baseline characteristics will be adjusted for in the model by including any statistically significant demographic and baseline characteristics as covariates in the logistic regression model.

Additional primary analyses include:

Re-intubation required (no/yes)

- a. Within 24 hours
- b. From 24-48 hours
- c. From 48-72 hours
- d. >72 hours but ≤ 7 days

The same methods used for the primary analyses will be repeated for these additional primary outcomes (within 24, 24-48, 48-72, and >72hrs) for the ITT population; and these analyses will also be repeated for the PP population (within 24, 24-48, 48-72, and >72hrs).

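### Section 7.1.1 fits the primary adjusted logistic model in four separate reintubation windows but names no sparse-data method for windows likely to hold few events (minor)

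*Combined protocol and SAP*

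**What the plan says.** Section 7.1.1 names one primary analysis: "The primary analysis is comparison of the groups on reintubation rates within 72 hours on the ITT population". It is a logistic regression, adjusted by "including any statistically significant demographic and baseline characteristics as covariates in the logistic regression model". No maximum number of covariates is set.

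The same section then lists, as additional primary analyses, reintubation (no/yes) within 24 hours, from 24 to 48, from 48 to 72, and after 72 hours up to 7 days. For these, the "same methods used for the primary analyses will be repeated for these additional primary outcomes (within 24, 24-48, 48-72, and >72hrs") in ITT and then in the per-protocol set. Section 7.1 applies one threshold throughout: "Results will be considered statistically significant if the p-value is less than or equal to 0.05".

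The plan does have a small-count rule. Section 7.1 switches from chi-square to Fisher's "exact tests if the data in the contingency table have cells with expected frequency of" less than 5, and says that these general methods are for demographics and baseline characteristics. Section 7.1.2 repeats the rule for in-hospital mortality and 30-day readmission. Section 7.1.1 has no counterpart for the logistic models.

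The windows are not in the endpoint table of Section 2.1, which lists "Proportion of patients that require reintubation within 72 hours" and "Association between reintubation rates and patient demographics or characteristics". Nor are they in the Section 4 aims, where Aim 1 is to "Compare reintubation rates (within 72 hours) between patients that undergo a standardized, intermittent NIV/HFNC protocol and a historical control cohort".

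**The concern.** Splitting a binary outcome into windows divides its events among several models, while each model keeps the full covariate list. Ordinary maximum-likelihood logistic regression has no finite group odds ratio when one group has no event. When both groups have one or two, it gives a very unstable one.

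The authors foresaw small cells for mortality and readmission but gave no rule for the outcomes likely to be sparsest. If a window model fails, the replacement will be chosen after the data are seen.

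The stake is limited but real. Section 3.1 says the data will be used to plan a randomized trial, and the intervention lasts about 24 hours (Section 6.5.2.2), so the timing of failure is useful planning information.

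**Working it through.** The plan gives no power or event-count figure to reproduce.

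**Inputs from the documents**
- Group sizes: 40, and up to 80 (Section 5).
- Reintubation rates cited in Section 3.2: 12-14% of planned extubations generally; 23% and 19% in a randomized trial of high-risk patients; 35-67% in patients aged 65 or over with severe chronic cardiac or respiratory disease.

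**Assumptions (not in the documents)**
- Same risk in both groups.
- 72-hour events split 50/30/20 over the three days.
- 3-10% of all patients reintubated after 72 hours and by day 7.

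**Formulas.** For a window with risk p, expected total events = 120p. The chance that at least one group has no event is 1 - [1 - (1-p)^40] x [1 - (1-p)^80].

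**48-72 hours**
- 72-hour rate 23%: p = 0.23 x 0.20 = 0.046. Expected events: 5.5 in total, 1.8 in the group of 40. 0.954^40 = 0.152 and 0.954^80 = 0.023, so the chance is 1 - 0.848 x 0.977 = 0.17.
- 35%: p = 0.07. Expected events: 8.4 in total. 0.93^40 = 0.055 and 0.93^80 = 0.003, so the chance is 0.06.
- 14%: p = 0.028. Expected events: 3.4 in total. Chance 0.39.
- 67%: p = 0.134. Expected events: 16.1 in total. Chance 0.003.

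**After 72 hours to day 7**

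| Assumed risk | Expected events, total | (1-p)^40 | (1-p)^80 | Chance that a group has none |
|---|---|---|---|---|
| 3% | 3.6 | 0.296 | 0.087 | 0.36 |
| 5% | 6.0 | 0.129 | 0.017 | 0.14 |
| 8% | 9.6 | 0.036 | 0.001 | 0.04 |
| 10% | 12.0 | 0.015 | 0.0002 | 0.015 |

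**Earlier windows and the primary endpoint.** At 23%, the 24-48 hour window (p = 0.069) gives 6% and the first 24 hours (p = 0.115) under 1%. For the 72-hour endpoint the chance is about 0.2% at a 14% rate and negligible at 23% or more.

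**Sensitivity for 48-72 hours at 23%**
- If only 10% of the 72-hour events fall in this window (p = 0.023), the chance is 0.49. If one third do (p = 0.077), it is 0.04.
- With 60 controls: 0.954^60 = 0.059, so 1 - 0.848 x 0.941 = 0.20. With 40 controls: 1 - 0.848 x 0.848 = 0.28.

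**How much a late window can say.** The exact 95% interval for 0/40 is 0 to 8.8%. The conditional exact odds-ratio interval is 0 to 3.0 for 0/40 against 4/80, and 0.02 to 19.8 for 1/40 against 2/80.

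**Does a penalised fit cure the failure?** Trials were simulated with two assumed covariates (one binary, 40% against 20%; one continuous, shifted by 0.4 SD), 600 replicates per scenario. Firth-penalised fits converged in every replicate, and the largest absolute group log odds ratio was 3.9.

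**The case against.** **Frequent failure.** A reader might infer that the window models will usually break down. Taken over the three later windows together, the chance that some window has an empty group is 50% at 23% with 3% late. That is a composite. At 23% with 5% late the separate windows give 6%, 17% and 14%, so most single models would have events in both groups. The late figure also falls from 36% to 1.5% across the assumed range, and the 14% rate is for planned extubations generally, not this population. This objection stands: the documents support few events, not routine failure.

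**Covariates.** The uncapped list could be blamed for non-finite estimates. In the simulation it hardly mattered: 51% with two covariates against 50% with none at 23%/3%, on the same composite. Few covariates are still advisable with about five events, but the empty cell causes the failure.

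**Multiplicity.** A reader might infer inflated error, since five ITT tests at 0.05 give 1 - 0.95^5 = 0.23 if independent. The tests are correlated, Section 7.1.1 names a single primary analysis, and the study is exploratory. The label is untidy, no more.

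**Counting.** A reader might infer that the denominator is undefined after an earlier reintubation, death or discharge. A no/yes outcome on the ITT set, with the inclusion rule in Section 6.6, points to all patients, with no reintubation in the window counted as no. What is missing is one clarifying sentence.

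**What remains.** The Fisher wording in Section 7.1 could be read as a general rule, but Section 7.1.1 explicitly prescribes logistic regression for every window. No sparse-data method is named for those models.

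**Conclusion.** The point holds, as a minor one. The plan commits four windows, in two analysis sets, to ordinary adjusted logistic regression without saying what happens when events are few. Under the assumed timing and equal risks, at a 23% 72-hour rate, the group odds ratio would be non-finite in about one trial in six for 48-72 hours. For the last window the range is from about one in three to one in seventy. At 35% the 48-72 hour figure is about 6%, and at 67% it is negligible. The conclusion is sensitive to the timing split and the late rate, neither of which the documents give. The 72-hour primary analysis is untouched.

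**What to change.** In Section 7.1.1:

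1. Fit the four window models, in ITT and per-protocol, by Firth-penalised logistic regression with a small covariate set, in place of ordinary maximum likelihood.
2. Show the count and percentage in each group, with an exact confidence interval, beside each model result.
3. Call the four windows supportive of the single 72-hour ITT primary analysis.
4. As a clarification only, state that a patient with no reintubation in a window counts as no, on the whole ITT set.

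The cost is a change of SAP wording and slightly more analysis work, and the windows lose their primary label. Penalisation gives a finite estimate but adds no information, so the late-window intervals will stay wide.

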7.1.2 Secondary Statistical Analysis Methods

Total hospital length of stay, ICU length of stay, ventilator time, in hours, will be compared between groups using Wilcoxon rank sum tests, as the durations are expected to be markedly non-normally distributed and skewed.

In-hospital mortality and 30-day readmission rates will be compared between the groups using a chi-square test, or Fisher's exact test if the data in the 2x2 contingency table have cells with expected frequency of $n < 5$.

All secondary analyses will be completed on the ITT population.

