6.3 Participant Identification Procedures and Eligibility Criteria

6.3.1 Historical Control Group:

Reintubation rates are tracked at the institutional level as part of quality assessments; a delegated member of the study team will utilize this patient list to generate a study-specific subset of high-risk patients who were mechanically ventilated between February and October 2019. This list will be screened for the inclusion/exclusion criteria below by a delegated member of the study team. The study statistician or designee will then use a random number generator to generate a final group of 80 patients that meet inclusion criteria.

Inclusion Criteria

1. Age ≥ 18 years
2. Chronic cardiac or pulmonary condition
 - o COPD, history of based on any documentation notes
 - o CHF, history of based on any documentation notes
 - o Positive fluid balance, defined as a positive number when calculating fluid input minus fluid output over the approximate 24-hour-period prior to extubation
3. Documented modified RSBI between 58-105 on the day of extubation

Exclusion Criteria

1. Patients receiving comfort care or terminal extubation
2. Home ventilator, based on any documentation notes
3. Only primary extubations will be included (i.e., if the patient list query identifies multiple mechanical ventilations, only the primary encounter/event will be included)

6.3.2 Prospective Group:

An EMR-based report of all patients that have been on mechanical ventilation (MV) at Grant Medical Center for at least 24 hours will be generated daily (Monday through Friday), per standard procedure. Eligibility determination for this cohort will be conducted by a delegated member of the study team across two time points: pre-screening to determine eligibility to approach for consent, and eligibility on the day of extubation to determine enrollment eligibility (Appendix A). Only patients meeting all required eligibility criteria above will be enrolled to the study; any PHI collected for patients that are not subsequently enrolled will be destroyed after non-eligibility determination.

Pre-Screening Criteria:

1. No home ventilator, based on any documentation notes
2. Not scheduled for terminal extubation/comfort care
3. Has not had a failed extubation during the current hospital stay
4. Has not previously participated in the current trial

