6.4 Recruitment and Informed Consent (Prospective Group Only)

Patients are typically on mechanical ventilation for approximately 3-5 days, allowing several days from the time of identification for recruitment and consent. Because patients will be sedated and intubated, informed consent will be obtained from the patients' legally authorized representatives (LAR). Specifically, a member of the patient's care team will give each family of mechanically ventilated patients a recruitment card (Appendix B) and explain that a member of the research team will be approaching them to discuss the study. This ensures that the LARs are introduced to the study by the patients' care team.

The LAR will sign the informed consent document prior to any procedures being done specifically for the study only (i.e. above routine care). A copy of the signed informed consent document will be given to the LAR for their records, with a copy placed in the patient's medical record. Because patients may remain sedated following extubation, it may be not practicable to re-consent all patients following extubation. Patients in the Intensive Care Unit are assessed for confusion/delirium as standard of care using the Confusion Assessment Method for the ICU (CAM-ICU). Therefore, each patient's routine CAM-ICU score will be reviewed daily by a member of the study team. Those with negative CAM-ICU scores will be informed by a member of the study team that they were enrolled in a research study by their LAR, and the patient will be provided the opportunity determine whether they wish to remain enrolled in the study using the regained capacity portion of the consent form (Appendix C). Patients with positive CAM-ICU scores or who are transferred outside of the ICU (where CAM-ICU is not conducted) will not be re-consented. It is important to note that at this time all study interventions would have been completed; patient consent can only be obtained for continued data collection. Patients who do not wish to continue will be treated as outlined in [Section 6.6](#).

All informed consent procedures (initial and in the event of regained capacity) will be obtained and documented on an IRB-approved informed consent form (Appendix C) in accordance with the OhioHealth Research Institute (OHRI) policy for obtaining and documented informed consent.

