6.5.2.2 Study Standardized, Intermittent NIV/HFNC Protocol

Patients that **do** meet all study eligibility criteria will be placed in the standardized, intermittent NIV/HFNC protocol as outlined below. For NIV, OhioHealth Grant Medical Center routinely utilizes BiPAP, a non-invasive ventilator. For HFNC, OhioHealth Grant Medical Center utilizes a heated high flow generator, an oxygen blender, and a humidifier. Please see Appendix D for BiPAP/HFNC setup, monitoring, and clinical decision making guide and Appendix E for device specification sheets.

Briefly, over the 24-hour-period following extubation, enrolled patients will receive BiPAP for 2-hour intervals (e.g., 2 hours on, 2 hours off) during the day and continuously at night. During BiPAP breaks, patients will receive heated high flow nasal cannula (HFNC) oxygen. As such, the intervention portion of this study is limited to approximately 24 hours (the 24-hour-period following extubation).

- The treating physician or advanced practice provider will order the BIPAP settings and care according to current standard methods.
- The Respiratory Therapy Team will set up, turn on and take off the BIPAP. They will also discuss the patient's care on BIPAP at the start of each shift with the RN and monitor the BIPAP approximately every 3 hours.
- The registered nurse (RN)/respiratory therapist (RT) team is responsible for the routine care they provide these patients, including assessing and monitoring the patient while they are on BIPAP for the study. They will identify, document and inform the physician and RT if problems and/or escalation of patient care occur.

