8 SAFETY INFORMATION AND EXPECTED RISKS

This exploratory study is designed to obtain baseline information to support the potential effectiveness of a standardized postextubation management protocol, utilizing BiPAP and Heated High-Flow Nasal Cannula oxygen (HFNC). BiPAP and HFNC are routinely used at OhioHealth Grant Medical Center; the

research study proposed evaluates these therapies in combination, according to a standardized (2 hours on/2 hours off) protocol.

There are multiple potential physical risks associated with being hospitalized and on mechanical ventilation (Table 1). These risks are present regardless of postextubation management strategies, i.e., assignment to the standardized postextubation management protocol of interest is not considered to add additional risk beyond that associated with routine care. In order to monitor and minimize any potential risks, a Data Safety Monitoring Board (DSMB) will be utilized for this study as outlined in [Section 8.2](#).

Table 1 Potential Adverse Events (AEs) or Serious Adverse Events (SAEs).

Frequency	Mechanical Ventilation ^a	BiPAP/HFNC
Common	Acute lung injury (ALI) Acute respiratory distress syndrome (ARDS) Barotrauma Mortality Organ impairment (hepatic, renal, gastrointestinal, CNS) Sepsis Side-effects of medications (delirium, confusion, agitation) Ventilator-acquired pneumonia (VAP)	Aerophagia (aerophagy) Agitation or delirium Claustrophobia Congestion Dry mouth, nose, and/or throat Other (describe)
Uncommon	Decreased cardiac output Endotracheal tube complications Infection	Breathing difficulty Delayed reintubation
Rare	Damage to trachea, lips, tongue, teeth, vocal cords Tracheostomy	

^a Mechanical ventilation for all patients will be conducted per standard procedures. There are no changes to mechanical ventilation as a result of this research study. All risks associated with mechanical ventilation are present for all patients, regardless of whether or not they are enrolled into the study.

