9.2 Adverse Events

An adverse event is any untoward or unfavorable medical occurrence in a human subject, including any abnormal sign (e.g. abnormal physical exam or laboratory finding), symptom, or disease, temporally associated with the subject's participation in the research. As outlined above ([Section 9.1](#)), AEs that are unexpected, related or possibly related to the research *and* suggest increased risk will be reported to the OhioHealth IRB.

It is possible that research participants may experience adverse events that do not meet OhioHealth's mandatory reporting requirements (e.g., they are not unexpected, they are not possibly related to participation in the research, they do not place the subjects or others at greater risk of harm). Adverse events that do not meet reporting requirements will be reported to the Data Safety Monitoring Board (DSMB) for review during standing DSMB meetings and summarized for the IRB during the continuing review.

Importantly, for the current study, adverse events associated with mechanical ventilation cannot be related to the study intervention, as study-specific interventions do not occur until the patient is extubated. As such, mechanical ventilation-related adverse events that occur prior to the day of planned extubation will not be reported to the OhioHealth IRB.

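### Ventilator time, ICU stay and hospital stay are compared unadjusted as durations that include time before extubation, so a pre-treatment difference between non-randomised groups would be read as a difference in outcome

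*Combined protocol and SAP*

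**What the plan says.** Section 7.1.2 sets the test: "Total hospital length of stay, ICU length of stay, ventilator time, in hours, will be compared between groups using Wilcoxon rank sum tests". It names no covariates. Section 4 describes the same outcomes as totals: "Secondary aims include calculating length of stay (ICU and total hospital), total ventilator time". Section 2.1 lists ICU and total length of stay and ventilator time, with no time origin for any of them.

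Other sections fix when treatment can act. Section 9.2 says that "study-specific interventions do not occur until the patient is extubated". The footnote to Table 1 in Section 8 adds: "There are no changes to mechanical ventilation as a result of this research study". Section 6.5.2.2 confines the intervention to roughly the first day after extubation.

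Two figures bear on size. Section 6.4 states: "Patients are typically on mechanical ventilation for approximately 3-5 days". Section 2.1 gives "total hospital stay, estimated at 14.1 ± 16.9 days", taken from a cited source.

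The two groups enter differently. Under Section 6.3.2, prospective patients come from a daily report of those who "have been on mechanical ventilation (MV) at Grant Medical Center for at least 24 hours". The historical criteria in Section 6.3.1 state no minimum. Section 7.1.1 expects baseline differences and adjusts for them by logistic regression, but only for reintubation.

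**The concern.** A duration that starts before treatment mixes baseline history with outcome. For a patient who is not reintubated, total ventilator time is fixed before the study protocol begins: it is a baseline characteristic tested as an outcome. Both stays also contain the first ventilation episode.

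In a randomised trial the earlier time would mainly add noise. Here the controls are historical, the tests are unadjusted and the entry rules on ventilation time differ. Any group difference in time to first extubation would therefore pass straight into the reported comparison. Section 3.1 says the data will be used to plan a larger randomised trial, so a misattributed difference could carry into that design.

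**Working it through.** The plan gives no power or effect size for these outcomes, so there is no figure of its own to reproduce.

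**1. Share of mean ventilator time before extubation**

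Share = v / (v + p·x), where:
- v = days ventilated before first extubation. The 3-5 days of Section 6.4 stand in for this.
- p = reintubation rate. Section 3.2 gives 12-14% for planned extubations generally, 23% and 19% in a high-risk trial, and 35-67% in older patients with chronic disease.
- x = extra ventilator days if reintubated. The plan gives none; 3, 5 and 7 are assumed.

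| v | p | x | Share |
|---|---|---|---|
| 5 | 0.12 | 3 | 5 / 5.36 = 93% |
| 5 | 0.23 | 5 | 5 / 6.15 = 81% |
| 3 | 0.23 | 5 | 3 / 4.15 = 72% |
| 3 | 0.35 | 7 | 3 / 5.45 = 55% |
| 3 | 0.67 | 5 | 3 / 6.35 = 47% |
| 3 | 0.67 | 7 | 3 / 7.69 = 39% |

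Across p = 12-35% the range is 55-93%. On this grid the share falls below half only at p = 67% with v = 3 and x = 5 or 7.

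**2. Share of hospital stay**

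3 / 14.1 = 21% and 5 / 14.1 = 35%. Days in hospital before intubation are not given and would raise this. No ICU figure is given, so that share cannot be computed.

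**3. False rejection with no treatment effect**

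Simulated Wilcoxon tests on ventilator time, 40 v 80, two-sided 0.05 (the plan does not state sidedness). All distributions are assumed.

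*Set A.* Pre-extubation time is log-normal with median 96 h and log-SD 0.8; re-ventilation time has the same distribution; reintubation is 25% in both groups.
- Pre-extubation time 25% longer in one group: the total-time test rejects about 22% of the time.
- 50% longer: about 59%.
- Hours counted from extubation: about 5% in both cases.

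*Set B.* Log-normal with coefficient of variation (CV) 0.8; extra time averages 5 days if reintubated; reintubation is 23% in both groups.
- Pre-extubation means of 4 v 5 days: 24%. Means of 3 v 5 days: 81%. Counted from extubation: about 4-5%.
- A 24 h minimum in the prospective group alone, otherwise equal distributions:

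| Mean before extubation | CV 0.8 | CV 1.2 |
|---|---|---|
| 3 days | 10% | 37% |
| 4 days | 6% | 19% |
| 5 days | 5% | 12% |

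Counted from extubation, these stay at about 5%.

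**4. Does moving the origin gain power?**

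Under the Set A distributions, for reintubation of 35% v 17.5%, power is 14% on total ventilator time, 49% on post-extubation hours, and 52% for a chi-square test on reintubation itself. The rank correlation of post-extubation hours with reintubation (yes/no) is 0.97. At 23% v 19%, power is 5.5% on total time and 6.7% on post-extubation hours.

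**5. Hospital stay under an assumed effect**

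Total stay is modelled with mean 14.1 and SD 16.9 days, and the post-extubation part is halved by treatment (assumed).

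| Days before extubation | Power, total stay | Power, from extubation | Rank correlation of total with post part | With pre part |
|---|---|---|---|---|
| 3 | 80% | 89% | 0.93 | 0.29 |
| 5 | 57% | 82% | 0.82 | 0.47 |

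**The case against.** - **A reader might infer that all three outcomes are mostly pre-treatment history.** The documents support this only for ventilator time. About 65-79% of mean hospital stay lies outside first-episode ventilation, and in simulation total stay follows its post-extubation part more closely than the earlier part. The 14.1-day figure comes from a cited source and is not shown to fit this high-risk group. ICU stay cannot be judged.
- **A reader might infer that a large reduction in reintubation would be hidden.** It would not. Reintubation within 72 hours is the primary endpoint, analysed directly and with adjustment in Section 7.1.1, with further windows to 7 days.
- **A reader might infer that moving the origin gives a worthwhile power gain.** For ventilator time the gain is essentially the power of the reintubation comparison already planned, and it all but vanishes at 23% v 19%.
- **The imbalances are assumed.** This is fair: the plan gives no figure for any difference in pre-extubation time, so the rejection rates show sensitivity and do not predict what will happen.
- **The study is an exploratory pilot, and totals are useful resource measures.** Also fair. It argues for keeping totals as descriptive statistics; it does not justify testing them as outcomes between non-randomised groups.
- **The data collection tools (Appendices A and F) and the worksheet (Appendix G) may define the durations.** Their content is not in the text available. Section 4 nevertheless says total ventilator time, and the analysis section should carry any different definition.

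**Conclusion.** The point holds as a bias problem in the secondary analyses. As written, all three durations are totals or have no stated origin, and all are compared unadjusted between groups that may differ in time before extubation.

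The share the intervention cannot affect is 55-93% of mean ventilator time at 12-35% reintubation, given the assumed 3-7 extra days. It is about 21-35% of mean hospital stay, leaving out any days before intubation, and unknown for ICU stay. That ventilator time is wholly pre-treatment in patients not reintubated follows from the text and needs no assumption. The false-rejection rates rest on assumed log-normal durations and assumed imbalances, and are illustrative.

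The primary endpoint is timed from extubation and is unaffected.

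**What to change.** In Sections 2.1, 4 and 7.1.2:

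1. Count ventilator hours, ICU stay and hospital stay from the first planned extubation, with ventilator hours set to 0 for a patient not reintubated.
2. Report ventilator, ICU and hospital time before that extubation in the baseline table, by group.
3. Keep the totals as descriptive statistics, without tests.
4. State that post-extubation ventilator hours largely restate the reintubation endpoint and are not independent evidence.

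Giving both groups the same 24-hour minimum would remove one source of imbalance, but would leave pre-treatment time in the outcome, so it does not replace step 1.

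The cost is mainly wording. The reintubation windows in Section 7.1.1 already need extubation and reintubation times, and the stay outcomes need discharge times, so little or no new data should be required; this should be checked against the collection forms. The downsides are a less direct comparison with literature on total durations, eased by step 3, and a ventilator outcome with many tied zeros.
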